1.2.3 Exploratory Endpoint

a. Correlate the levels of PTEN immunostaining with response.

b. Correlate levels of phosphorylated AKT (pAKT) immunostaining with response.

c. Correlate expression of endothelial (CD105 and CD31/CD34) and pericyte (NG2, and MCAM [CD146]) markers in the initial diagnostic and final surgical specimens with response.

d. Determine translational (mRNA to protein) profiles by means of next-generation whole exome sequencing and sequencing of ribosome-protected mRNA associated with resistance to the investigational combination.

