7.3.3 Research biopsies

Formalin-fixed paraffin embedded tissue blocks from the patient's primary tumor collected for diagnostic purposes will be requested for all patients enrolled in the study at the time of registration. In addition, a research biopsy will be obtained at baseline, on cycle 2 day 1, and at the time of surgery if residual tumor. The goal is for 2-4 core biopsy specimens obtained using standard institutional guidelines for a diagnostic core biopsy of a breast mass. However, biopsy samples will preferably be obtained using a 14-18 gauge core needle. At least one core will be used to prepare a paraffin block (paraffin-embedded blocks or formalin fixed tissue) and at least one core will be immediately freeze (snap frozen individually for gene expression).

Snap frozen research biopsies will be sent to UAB Tissue Procurement where biopsies will be stored for batching. The batched biopsies will then be forwarded to HudsonAlpha Institute for Biotechnology. All samples will be indelibly labeled with the appropriate study number, and date of

acquisition; these data will be correlated with clinical efficacy including complete response and objective response. All samples sent to HudsonAlpha Institute for Biotechnology for comprehensive genomic analysis will be labeled with the appropriate study number only. Frozen research biopsy will be used for comprehensive genomic analysis such as Next-GEN genomic analysis. “Next-GEN genomic analysis will be done at HudsonAlpha Institute for Biotechnology in Huntsville, Alabama (Shared Facility of the UAB Comprehensive Cancer Center) by [name] group. No funding is necessary to conduct the evaluation in the laboratory at this time or macro-dissection; funds are needed only for shipping.

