7.3.4 Ribosomal profiling on the final surgical specimen

Fresh frozen, macrodissected surgical specimens collected and stored in RNAlater with the assistance of Tissue Procurement that meet criteria for expanded ribosomal profiling will undergo next-generation sequencing. We anticipate that small size of the residual tumor that is surgically excised will be the principal limiting factor in the conduction of this correlative study. Based on our previous experience^{1,2}, we project that in the course of the study approximately 8 surgical specimens will undergo expanded ribosomal profiling. Three samples of previously untreated hormone receptor positive and Her2 negative breast cancer matched for clinical and demographic characteristics with the study samples and 3 samples of normal breast tissue resected for indications other than cancer will undergo expanded ribosomal profiling following the same protocol. Both samples of untreated luminal breast cancer and normal breast tissue will be obtained from patients who will not participate in the study.

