10.2 Statistical Analysis

The primary analysis is of safety and will include any patients who receive at least one dose of the investigational regimen. The rate of adverse events will be estimated at the end of the study along with two-sided 95% exact CIs (Clopper-Pearson intervals). At the completion of the study, the secondary endpoint of pCR or downstaging rate will be estimated along with two-sided 95% CIs with the exact method of Clopper-Pearson intervals. Secondary endpoint analysis will be descriptive. Mean, median, geometric mean, range and coefficient of variation will be used to describe continuous demographic variables. Frequency and proportion will be used to describe categorical variables.

We will use descriptive statistics (mean, median, geometric mean, coefficient of variation, and 95% confidence intervals) and graphical displays (mean concentration-time graphs, scatter plots, box plots or spaghetti plots) to evaluate the pharmacokinetic parameters of the TRC105 and everolimus. We will use descriptive statistics (mean, median, geometric mean, coefficient of variation, and 95% confidence intervals) and graphical displays (scatter plots, box plots, plots of PD parameters against PK data) to analyze the changes in markers of proliferation and angiogenesis with the investigational treatment.

Exploratory analysis will be conducted on the correlations between clinical outcomes and pharmacodynamic biomarkers or translation profiles. Translational profiles will be analyzed between responders and non-responders and the differences between responders and non-responders will be presented in scatter plots along with corresponding 95% CI. Quartile normalization and logarithmic transformation will be conducted before analysis. Logistic regression analysis will be used to predict response with translational profiles or biomarkers with or without adjustment for covariates, e.g. age. Multivariate Cox proportional hazards model will be used to identify a set of biomarkers for prediction of response. Odds ratios with 95% CIs will be calculated for each significant biomarker in terms of predicting response. However, it is recognized that sample size may be too small for such analyses and these analyses are conducted only to generate hypotheses that will require further validation.

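### Ribosomal profiles from the surgical specimen are planned as predictors of response, but the tissue is post-treatment and its availability depends on the response

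*Combined protocol and SAP*

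**What the plan says.** Section 7.3.4 places ribosomal profiling of trial patients on macrodissected tissue from the final surgical specimen. It expects that "small size of the residual tumor that is surgically excised will be the principal limiting factor" and projects that "approximately 8 surgical specimens will undergo expanded ribosomal profiling". The comparators are 3 untreated tumours and 3 normal breast samples, all from people outside the trial. The section describes no baseline or cycle 2 day 1 ribosomal profile.

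Section 10.2 then says "Translational profiles will be analyzed between responders and non-responders", with the differences shown in scatter plots with 95% confidence intervals. It continues: "Logistic regression analysis will be used to predict response with translational profiles or biomarkers". Its caveat is that the sample may be too small and that the results only generate hypotheses.

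Endpoint 1.2.3c correlates endothelial and pericyte "markers in the initial diagnostic and final surgical specimens with response". Section 7.3.3 collects research cores at baseline, at cycle 2 day 1 (C2D1) and "at the time of surgery if residual tumor".

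Section 10 names the efficacy endpoints as pCR or downstaging, and section 1.2.2 assesses them at surgery. Section 7.2.4 defines pCR as no residual invasive cancer in the breast or sampled nodes.

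**The concern.** A predictor of response should be measured before the response, in patients whose inclusion does not depend on it. A ribosomal profile under section 7.3.4 meets neither condition. It comes from tumour that has already been through treatment, and it exists only if treatment left enough tumour to profile. The patients with the deepest responses are the ones who cannot contribute.

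The exploratory objective (1.1.3) seeks biomarkers potentially predictive of response or resistance. If the planned model is reported as written, a feature of residual tumour could be presented as something that would have identified responders in advance. More patients would not cure this, so the sample-size caveat in section 10.2 does not answer it.

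**Working it through.** **Stated figure.** The only figure in the plan that bears on this is the projection of about 8 specimens. It is attributed to previous experience without inputs, so it can be neither reproduced nor refuted.

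**Step 1: order in time.**
- Profile: final surgical specimen, after the neoadjuvant course (7.3.4).
- pCR or downstaging: determined at that same surgery (1.2.2, 7.2.4).
- Clinical and imaging response: recorded during treatment (7.2.4).

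On any of these definitions, the profile does not precede the outcome.

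**Step 2: availability.** A patient with pCR has no invasive tumour to profile. Below pCR, availability depends on residual size. Section 7.3.4 mentions criteria for profiling but states no minimum size.

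**Step 3: share of the trial** (26-38 patients, section 4.3). 8/38 = 21%; 8/26 = 31%. Against the 20 phase II patients alone, 8/20 = 40%.

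**Step 4: how many of the 8 might be responders.** Take responder to mean downstaged to stage 0/1, with pCR counted inside that group. As scenarios only, use the rates that section 2.1.5 cites for letrozole plus bevacizumab: 45% downstaging with 11.1% pCR (randomised study), and 32% stage 0/1 with 12% pCR (pilot). R is the number of responders and C the number with pCR, both rounded to whole patients.
- Random draw from all patients: 8R/N
- Random draw from patients without pCR: 8(R − C)/(N − C)
- Largest residual tumours first, with downstaged tumours assumed smaller: max(0, 8 − (N − R))

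| Rates | N | R | C | N − R | From all | From non-pCR | Largest first |
|---|---|---|---|---|---|---|---|
| 45%, 11.1% | 20 | 9 | 2 | 11 | 8×9/20 = 3.6 | 8×7/18 = 3.1 | 0 |
| 45%, 11.1% | 38 | 17 | 4 | 21 | 8×17/38 = 3.6 | 8×13/34 = 3.1 | 0 |
| 32%, 12% | 20 | 6 | 2 | 14 | 8×6/20 = 2.4 | 8×4/18 = 1.8 | 0 |
| 32%, 12% | 38 | 12 | 5 | 26 | 8×12/38 = 2.5 | 8×7/33 = 1.7 | 0 |

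Losing the pCR patients alone lowers the expected number of responder profiles by between 0.5 and 0.8. Zero arises only under the assumed size ordering, because the non-responders alone then exceed 8.

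**Step 5: dependence on the definition.** If responder means pCR, no responder can be profiled at any N. If it means objective response, which sections 7.3.3 and 7.2.6 would allow, selection is weaker. In the pilot, 17 of 25 had an objective response and 3 had pCR, so at least 17 − 3 = 14 of those 17 had residual invasive disease in breast or nodes. Section 10.2 does not say which definition applies.

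**The case against.** The strongest reply is that sampling on the outcome does not by itself bias a logistic odds ratio; case-control studies rely on this. That is correct. A reader might infer that any odds ratio from these data must be wrong, but the documents do not support that. Bias would require tissue availability to depend on the profile within a response category. That is plausible, since residual size may track biology, but nothing in the plan establishes it. What remains is that the measurement is post-treatment, and that responders with pCR are missing altogether, so at best the contrast describes responders short of pCR.

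A reader might also infer that the responder group will be empty or nearly so. Downstaged patients with residual stage 1 disease can supply tissue, so apart from pCR the expectation is under-representation, not absence.

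A third tempting inference adds the cited 11.1% pCR and 8% near pCR (20 × 0.191 = 3.8) and concludes that about 4 of 9 phase II responders would lack usable tissue. This needs near-pCR patients to be downstaged as well, although section 7.2.4 defines near pCR by the breast residual alone. It also needs 0.5 cm or less to be too little tissue. The documents give neither.

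The scope is narrower than all biomarkers. Endpoint 1.2.3c names the initial diagnostic specimen too, and section 7.3.3 also runs this immunohistochemistry on earlier tissue. The synopsis lists translational profiling under research biopsies, which might suggest earlier samples, but section 7.3.4 is the specific text for ribosomal profiling.

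Finally, endpoint 1.2.3d speaks of profiles associated with resistance, for which residual tumour is a reasonable source. The fault is the use in section 10.2 to predict response, not the assay.

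**Conclusion.** The point holds for ribosomal profiles and for markers read on the surgical specimen. Taken after treatment and available only where tumour remains, they cannot support a claim to predict response, and the plan does not acknowledge this.

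In size, the point concerns about 8 profiles, or 21-31% of the expected enrolment. Responders without pCR might supply roughly 2 to 3 of the 8 if tissue were drawn at random from non-pCR patients, and none under the assumed largest-first ordering. These splits rest on rates from a different regimen and on a pCR-or-downstaging definition. Only the absence of pCR patients is certain.

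Severity is minor. The analyses are exploratory, are declared hypothesis-generating, and affect no primary or secondary endpoint.

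**What to change.** In section 10.2:

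- Limit every model that predicts response to tissue taken before the outcome: the diagnostic block and baseline cores, with C2D1 cores labelled as early on-treatment.
- Remove surgical-specimen ribosomal profiles and surgical immunohistochemistry from those models. Report them descriptively as features of residual or resistant disease, with ribosomal profiles set against the 3 untreated tumours and 3 normal samples.
- State which response definition the exploratory analyses use.
- Tabulate, by response category, how many patients did and did not supply usable tissue.

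In endpoint 1.2.3c, separate the diagnostic-specimen correlation from the surgical-specimen description. Align the synopsis with section 7.3.4 on which tissue is profiled.

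The cost is wording only. The diagnostic blocks and the baseline and C2D1 cores are already collected, so no new biopsy or assay is needed. The downside is that ribosomal profiling no longer supports a response-prediction claim.

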4.2 Phase II, expansion phase

The second part of the study (phase II, **expansion phase**), will ensue once the MTD and RP2D have been determined. The objectives of the dose expansion phase is to estimate the rate of complete pathologic remission (pCR) or downstaging in addition to continue evaluation of the safety. In order to minimize exposure of patients to ineffective therapy, Gehan’s two-stage design will be used⁵¹. The study will enroll 10 patients first, and if no patient has pCR or downstaging, the study will close on the basis that it is unlikely (p=0.1074) that 0/10 responses would occur if the true response rate were >20%. If at least one patient has pCR or downstaging, an additional 10 patients will be treated (total of 20). For patients enrolled in Phase II, dose of everolimus can be de-escalated down to 2.5mg if needed. No further de-escalation is allowed. If 2.5mg not tolerated then the patient will be removed from study.

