4.3 Study accrual and treatment considerations

It is anticipated that 26 – 38 patients will be enrolled in the study and accrual is expected to be completed in 24 months (see Section **10. STATISTICAL CONSIDERATIONS**). Patients meeting the eligibility criteria and who have signed the consent form will start Letrozole 2.5 mg PO daily, Everolimus 5 or 10 mg PO daily, and TRC105 15 or 10 mg/kg IV every two weeks with the first infusion administered in 2 split doses on days 1 (3 mg/kg) and 4 (12 mg/kg or 7 mg/kg), respectively. Premenopausal women at the time of study enrollment will receive goserelin 3.6 mg subcutaneously q 4 weeks to achieve ovarian suppression. A cycle is defined as 4 weeks of treatment. Breast ultrasound, will be conducted upon completion of each cycle to complement clinical assessments of the size of the tumor(s). The duration of neoadjuvant therapy is 24 weeks or 6 cycles. No extensions of the neoadjuvant therapy beyond 6 months are allowed. After neoadjuvant therapy, patients will undergo surgical treatment and will receive adjuvant therapy (radiation therapy, chemotherapy, hormonal therapy) according to the standard of care or at the discretion of the treating physician. The accrual rate is projected to be approximately 1-2 patients per month. Accrual will be halted as a result of any grade ≥ 3 hemorrhage, cerebrovascular and vasovagal adverse events; FDA will be contacted to discuss further accrual or potential need for protocol amendment.

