10.1 Sample Size and Power Justification

A. The dose escalation part of the study will follow a conventional 3+3 dose escalation design according to the schema above. We anticipate that up to 18 patients will be enrolled in this part anticipating that dose level 1 or 2 will be the RP2D. The number of patients to be enrolled ranges from 3 (if $\geq 2/3$ DLTs in cohort 1) to 18 (if enrollment of 6 patients in all cohorts).

B. The sample size of 20 in Phase II part study is NOT determined by the statistical power but the feasibility and relative precision of estimate, e.g. standards error of the estimation is $\leq 10\%$. We will estimate the pCR of the combination to generate hypotheses for further clinical investigations. In order to minimize exposure of patients to ineffective therapy, Gehan’s two-stage design will be used⁵¹ which allows for the rapid rejection of an ineffective treatment at the end of the first stage, and provides an estimation of the success rate with a given precision, at the end of the second stage. The study will enroll 10 patients first, and if no patient has pCR or downstaging, it is unlikely ($p=0.1074$) that 0/10 responses would occur if the true response rate were $>20\%$. If responses were 0/10, the phase II portion will be closed. If at least one patient has pCR or downstaging, an additional 10 patients will be treated (total of 20). With an accrual of 20 patients to phase II portion of the study, estimated two-sided 95% confidence intervals (CI) would be 1.2%-31.7%, 5.7% -43.6% and 11.8%-54.3% if pCR is 10%, 20% or 30% respectively. The confidence intervals are calculated using the exact method Clopper-Pearson intervals⁵⁴.

Table 10-1 shows the probability of early termination and observing one response or at least one response at the first stage ($N_1=10$).

Table 10.1: Probability of early termination and observing one response or at least one response at the first stage ($N_1=10$)

True ORR	Probability of having zero response ($x=0$)	Probability of having one response ($x=1$)	Probability of having at least one response ($x\geq 1$)
----------	---	--	---

0.1	0.3486	0.3874	0.6513
0.2	0.1074	0.2684	0.8926
0.30	0.0282	0.1211	0.9718

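### With few responders, the logistic models in Section 10.2 may yield no finite odds ratio, and reporting only significant markers can, under a Wald test, omit the strongest ones

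*Combined protocol and SAP*

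**What the plan says.** Section 10.2 (Statistical Analysis) states: "Logistic regression analysis will be used to predict response with translational profiles or biomarkers with or without adjustment for covariates, e.g. age". It then filters what is reported: "Odds ratios with 95% CIs will be calculated for each significant biomarker in terms of predicting response". It names no penalised or exact version of the model, no test (Wald, likelihood ratio, score or exact), no significance level, and no rule for a model that fails to converge. Exact intervals are specified in the same section for the adverse-event rates and for the rate of pCR or downstaging, but not here.

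The section does carry a caveat: "it is recognized that sample size may be too small for such analyses and these analyses are conducted only to generate hypotheses".

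The numbers available come from three places:
- Section 10.1: "The sample size of 20 in Phase II part study is NOT determined by the statistical power". Its precision is illustrated with intervals "if pCR is 10%, 20% or 30% respectively".
- Section 4.3: "It is anticipated that 26 – 38 patients will be enrolled in the study", over both parts of the study.
- Section 7.3.4: "approximately 8 surgical specimens will undergo expanded ribosomal profiling".

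**The concern.** When a marker splits responders from non-responders completely, or nearly so for a binary marker (quasi-separation), the logistic likelihood has no maximum. The fitted log odds ratio grows without limit and its standard error grows faster, so the Wald statistic goes to zero and the Wald p-value towards 1. Short of separation, the maximum-likelihood log odds ratio is biased away from zero in small samples.

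The exploratory objective is to find markers of response or resistance. A method that cannot give an estimate for the cleanest marker, overstates others on average, and prints odds ratios only for those passing an unnamed test can distort the list of hypotheses carried forward.

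**Working it through.** **1. The plan's own figures reproduce.** P(0 of 10 responses at a 20% rate) = 0.8^10 = 0.1074, as stated. Clopper-Pearson intervals for 2, 4 and 6 of 20 are 1.2–31.7%, 5.7–43.7% and 11.9–54.3%, matching Section 10.1 apart from last-digit truncation. The plan gives no figure for the logistic models.

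**2. Number of responders.** 20 × 10%, 20%, 30% = 2, 4, 6. These rates illustrate precision for pCR; they are not planned counts. Other values the documents allow: 45% downstaging with letrozole-bevacizumab (Section 2.1.5) gives 20 × 0.45 = 9. The 68% objective response in the pilot (same section) gives about 14 responders and 6 non-responders, so the scarce group is again 6. Pooling 38 patients at 20% gives 38 × 0.20 = 7.6, about 8.

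**3. Binary-marker examples, 4 responders of 20.**

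| Marker positive (responders; non-responders) | Wald p | Ordinary LR p | Fisher p | Firth OR (Wald-type 95% CI) |
|---|---|---|---|---|
| 4/4; 0/16 | 0.9996 | 0.000008 | 1/C(20,4) = 1/4845 = 0.0002 | 297 (5.1 to 17,153) |
| 4/4; 4/16 | 0.996 | 0.003 | C(8,4)/C(20,4) = 70/4845 = 0.014 | 25 (1.1 to 563) |

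For a 2×2 table, Firth's estimate adds 0.5 to each cell: (4.5 × 16.5)/(0.5 × 0.5) = 297 and (4.5 × 12.5)/(0.5 × 4.5) = 25. The maximum-likelihood odds ratio is infinite in both rows.

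**4. Simulation.** Assumptions: 20 patients, one normal marker, responders shifted by d SD (so the true log odds ratio per SD is d), two-sided 5% level. The values of d are assumed. Figures are percentages of trials detecting the marker; ranges cover independent runs of the same design.

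| Responders | True log-OR | Wald | Ordinary LR | Firth penalised LR |
|---|---|---|---|---|
| 4 | 1.0 | 10–11 | 45–46 | 36–39 |
| 4 | 1.5 | 18–21 | 76–79 | 68–70 |
| 4 | 2.0 | 21–23 | 95–96 | 90–93 |
| 6 | 2.0 | 50–55 | 98 | 96–97 |
| 2 | 2.0 | 0 | 79 | 63–68 |

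- Separation: about 1–6% of trials at 1.0; about 35%, 16% and 11% at 2.0 with 2, 4 and 6 responders.
- Mean log-OR in non-separated fits, true 1.0: about 1.4–1.6. On the odds-ratio scale, e^1.0 = 2.7 becomes e^1.4 = 4.1 to e^1.6 = 5.0. The median with 4 responders is 1.11. Firth's mean is 1.01–1.05.
- Type I error: ordinary LR about 7–8% with 4 responders (one run gave 8.7% with 2 and 4.9% with 6); Firth 3–5%.

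**5. About 8 specimens.** With 25–50% responders, one marker separates in 21–28% of samples at a true OR of 3 per SD and 44–50% at 6. No non-separated fit reached Wald p < 0.05.

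**6. Larger or more balanced samples.** With 9 of 20 expected responders, separation is 0.6% at OR 3 and 6% at OR 6. With 38 patients it is 0.2% and 2% at a 20% response rate, and 2% and 9% at 10%. With 38 patients and 8 responders, Wald detects 64/93/92% at 1.0/1.5/2.0 against 66/95/99.8% for Firth.

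**The case against.** The strongest reply is that the loss of detection belongs to the Wald test, which the plan never names. That is correct. The ordinary likelihood-ratio test keeps separated markers and detects slightly more often than Firth's method, partly because it is anti-conservative with very few responders. A reader might infer that ordinary logistic regression will drop a perfectly discriminating marker, or that Firth's method brings a large gain in power. The documents support neither: the first holds only if Wald is used, and the gap to Wald is mainly a difference between tests. The likelihood-ratio test still leaves a separated marker with an infinite odds ratio and no upper limit, so the promised estimate and interval cannot be given.

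Other points that stand:
- The 2 to 6 responders are near the low end. The stage rule in Section 4.2 counts pCR or downstaging, and the synopsis says the final analysis includes all enrolled patients. Pooling makes the problem small for immunohistochemistry and serum markers. It does not enlarge the 8 profiled specimens.
- For translational profiles, Section 10.2 also plans scatter plots of responder and non-responder differences with intervals, where a clean split would show. That provision does not extend to the other biomarkers.
- With 8 specimens and 2 responders, an unrelated transcript separates by chance with probability 2/C(8,2) = 2/28 = 7.1%. This is a multiplicity problem. Firth's method gives such false leads finite odds ratios but does not remove them.
- The analyses are exploratory and the small sample is disclosed. The caveat concedes imprecision, but does not say what to do when an estimate does not exist and does not lift the reporting filter.

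**Conclusion.** The point holds in a limited form. If the logistic models are fitted to about 20 patients with 2 to 6 responders (or as few non-responders), or to about 8 specimens, unpenalised estimation sometimes gives no finite odds ratio and overstates the mean log odds ratio in the rest. With 20 patients, separation is uncommon at a moderate effect (about 1–6%) and material at a strong one (11–35%). If Wald p-values decide significance, the reporting rule can remove the strongest candidates.

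It would go too far to say that estimates are generally infinite or inflated: medians are near the truth at a log odds ratio of 1.0, and null markers are not inflated on average. Nor is any dose decision, stopping rule, or primary or secondary estimate affected. The size rests on assumed marker effects, on reading the absence of any named method as ordinary maximum likelihood, and on which patients and which definition of response are used, neither of which Section 10.2 fixes. The change is worth making because it costs little, but the trial's main conclusions do not depend on it.

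**What to change.** In Section 10.2:
- Replace the logistic regression with Firth penalised logistic regression, using profile penalised-likelihood tests and 95% confidence intervals, with one marker plus at most one covariate per model.
- Report the odds ratio and interval for every marker analysed, not only those called significant.
- State which patients are included and which definition of response applies.

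This needs wording and standard software only; no new data. The cost is mild shrinkage towards no effect and somewhat lower detection than the anti-conservative ordinary likelihood-ratio test. Chance findings across many transcripts need a separate multiplicity statement.
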